5.7.4 Exploratory Analysis: SCRI with a Pre-vaccination Control Interval

The study will compare the rate of AESI in the risk intervals after the first dose and all doses combined with those in the pre-vaccination control interval in a conditional Poisson regression that estimates incidence rate ratio (IRR).

When sample size permits, subgroup analyses by age group, sex, race/ethnicity, and nursing home residency status will be performed.

5.7.4.1 Sensitivity Analyses for the Exploratory Analysis

To assess bias by factors that may affect the likelihood of subsequent vaccination, when the period prior to the vaccination is considered as the comparison or control interval, the following sensitivity analyses will be conducted to evaluate validity and robustness of the risk estimates:

- *Cases with comorbidities that are risk factors for the AESI and increase the likelihood of COVID-19 vaccination.* Using a pre-vaccination control interval is likely to overestimate the incidence risk ratio (IRR) because as more patients with the risk factors are vaccinated, more patients are likely to develop the AESI in the post-vaccination period (risk interval). Stratified analysis by major risk factors will be considered to assess the impact of such a bias.
- *Cases with comorbidities that are risk factors for the AESI and reduce the likelihood of COVID-19 vaccination (healthy vaccinee effect).* When there are pre-existing comorbidities which preclude

vaccination, using a pre-vaccination control interval is likely to underestimate the IRRs as there will be a deficit of patients who are at high risk of AESI in the risk interval. To address this issue, the incidence of the AESI prior to vaccination by day will be plotted to look for a potential drop in proximity to COVID-19 vaccination. A different length of the pre-exposure window will be excluded based on empirical data. Stratified analysis by major risk factors will be considered to assess the impact of such bias.

- *Cases have an increased probability of death pre-vaccination.* If the occurrence of AESI (e.g., PE, AMI, DIC, or ITP), existing comorbidities, or living in a nursing home increases the risk of mortality²⁴ in the pre-vaccination control interval, vaccinations that might have otherwise occurred after the event will never occur nor be known. These “cases” will not be included in the study due to lack of observation of the risk interval, and this scenario leads to an artificial deficit of the cases during the control interval, leading to an overestimated risk. The study will conduct SCCS with post-vaccination control intervals and the additional sensitivity analysis addressing curtailed observation time.

To assess the robustness of risk and control intervals, the study will explore different lengths of the risk and control intervals with clinical input and consideration of empirical data from temporal clustering. For example, two times the length of the risk interval (Table 3) for the control interval is considered for greater statistical power, although the likelihood of potential time-varying confounding is higher, given the longer observation period.

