5.1 Self-Controlled Methods

The SCCS design^{12,13} compares the incidence of adverse events within periods of hypothesized excess risk due to exposure (risk interval) with incidence during all other times (control interval). In SCCS, only cases

(i.e., individuals with an incident AESI) occurring during the study observation period are sampled, with estimation of risk occurring within individuals rather than between individuals. Created to assess the risk of acute events in clearly defined risk intervals, this design implicitly controls for measured and unmeasured time-invariant confounding as each case serves as his/her own control. To address the concern that the occurrence of the AESI may possibly affect the likelihood of subsequent vaccination, we will limit the control intervals for the primary analysis to post-vaccination only. To minimize exposure misclassification, we will restrict the study population to cases receiving COVID-19 vaccines.

The SCRI design is a special case of SCCS. In SCRI, a person's risk of experiencing the outcome immediately after exposure (risk interval) is compared to the same person's risk of experiencing the outcome in a discretely defined period (control interval), during which the occurrence of AESI is deemed to be unrelated to the exposure. Unlike the standard SCCS design, the SCRI method requires defining a specific time interval within the observation period as the control interval. Compared to SCCS, SCRI may be less affected by time-varying confounding due to the shorter control interval, while the shorter control interval may reduce statistical power.

The control intervals in both designs can be defined as pre- and post-vaccination, and both have strengths and limitations. A pre-vaccination control interval can facilitate timely analyses. However, the pre-vaccination control interval is subject to bias if the occurrence of the AESI affects the probability of subsequent vaccination, biasing the relative incidence in either direction. If the event only temporarily delays vaccination or increases the probability of vaccination, a pre-exposure period can be excluded to reduce the healthy vaccinee effect. Post-vaccination control intervals will avoid such a bias of reverse causation but require additional data accrual after the post-vaccination risk window, resulting in an analysis delay; the delay of the analysis is greater for AESI with longer risk intervals.

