5.2 Overview of Study Design

This protocol will use the SCCS design with post-vaccination control intervals as the primary analysis. This design is not subject to the bias from depletion or enrichment of AESI cases in the pre-vaccination control interval. However, it relies on an accurate definition of the risk window, which remains unknown following COVID-19 vaccination for each AESI. Inaccurate attribution of cases to the risk or control intervals may bias the risk estimate in either direction based on the shape of the underlying risk function of the AESI following vaccination. For example, for events with a late onset, attributing cases to the control intervals that should have been attributed to the risk interval may underestimate the relative risk. Sensitivity analyses, such as temporal scan, are proposed in Sections 5.7.2.1 and 5.7.3.1 to assess the robustness of risk intervals. Also, using post-vaccination control intervals will require additional data accrual following the post-vaccination risk interval, and this will delay the analysis.

The secondary analysis will use the SCCS design with control intervals around vaccination, including pre- and post-vaccination time other than the pre-specified risk interval (Table 3), during the observation period. This design has greater statistical power, compared with the primary analysis, by including more AESI cases. However, it is subject to the reverse causation bias from depletion or enrichment of AESI cases in the pre-vaccination control interval because the occurrence of an AESI during the observation period may affect the likelihood of subsequent vaccination. For example, if an AESI reduces the probability of subsequent vaccination, the relative incidence associated with vaccination will be biased upwards. It is

also subject to the same bias as the primary analysis from inaccurate definition of the risk window in the post-vaccination period.

The exploratory analysis will use the SCRI design with only a pre-vaccination control interval. This design can provide more timely results, compared with the primary analysis. However, it is subject to the same reverse causation bias described above from depletion or enrichment of AESI cases in the pre-vaccination control interval. This analysis is performed for comparison purposes to understand the magnitude and direction of the potential bias this study design may create in the measure of association.

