5.6 Time-varying Confounding

Time-varying confounding may be of concern in the SCCS design with longer control intervals during the study observation period. Some AESI, including AMI, exhibit seasonal trends. In addition, given that COVID-19 has been associated with cardiovascular disorders, and the risk of exposure to COVID-19 varies throughout the study period, the risk of related cardiovascular AESI may vary during the study period.^{15,16} Adjustment for time-varying confounding will be considered based on their association with the individual AESI and addressed using statistical models if strong time-varying confounding exists. The SCRI design is less susceptible to time-varying confounding given the discrete and relatively short risk and control intervals.

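### Section 5.7.4.1 attributes SCRI bias to stable comorbidities that cancel within person, and gives the healthy-vaccinee effect a direction that conflicts with its own check

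*Protocol*

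**What the plan says.** Section 5.7.4.1 lists three sources of bias when time before vaccination serves as the control.

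- Bullet 1 (comorbidities that raise uptake): the incidence rate ratio (IRR) is overestimated "because as more patients with the risk factors are vaccinated, more patients are likely to develop the AESI in the post-vaccination period".
- Bullet 2 (comorbidities that lower uptake, labelled the healthy-vaccinee effect): "using a pre-vaccination control interval is likely to underestimate the IRRs as there will be a deficit of patients" at high risk in the risk interval. The check is a daily plot of pre-vaccination incidence, looking for a fall close to vaccination. The responses are a different excluded window and possible stratification by major risk factors.
- Bullet 3 (death before vaccination): cases are missing from the control interval and the risk is overestimated.

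Elsewhere the Protocol says:

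- Section 5.1: "this design implicitly controls for measured and unmeasured time-invariant confounding as each case serves as his/her own control", and "we will restrict the study population to cases receiving COVID-19 vaccines". A pre-vaccination control can go wrong by "biasing the relative incidence in either direction".
- Section 5.2: "if an AESI reduces the probability of subsequent vaccination, the relative incidence associated with vaccination will be biased upwards". Of the SCRI, "it is subject to the same reverse causation bias described above from depletion or enrichment of AESI cases in the pre-vaccination control interval". The SCRI is run to learn the size and direction of that bias.
- Section 5.6: "The SCRI design is less susceptible to time-varying confounding given the discrete and relatively short risk and control intervals".
- Section 5.7.2.1 places the baseline-risk offset among the sensitivity analyses of the primary model. Sections 5.7.3.1 and 5.7.4.1 do not list it.

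**The concern.** Bullets 1 and 2 reason as a cohort analyst would: who gets vaccinated changes how many events follow vaccination. In a within-person comparison of vaccinated cases, a fixed trait multiplies the rate in both intervals and drops out. Bullet 2 has a second problem. It places the deficit in the risk interval, but its check looks for a deficit before vaccination, which acts on the IRR in the other direction if it reaches the control interval.

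At stake is the reading of the exploratory and secondary comparisons. If the SCRI exists to show the direction of the bias, the text that says which mechanism pushes which way has to be right. Stratifying by hypertension or diabetes can show effect modification, but it cannot measure a bias that those traits do not cause.

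**Working it through.** **The plan's own arithmetic.** The Protocol gives no figure for this bias. Section 5.3 does give one for the same algebra: a control interval that captures 90% of its events, against a fully captured risk interval, yields 100%/90% - 1 = 11% overestimation. That is 1/(1-q) with q = 0.10, and it reproduces.

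**Set-up.** True IRR 1; control days -42 to -15 (28 days, ending 15 days before dose 1, Section 5.4.2); risk days 1 to 28 (Table 3). All prevalences, hazard ratios, probabilities and durations below are assumptions.

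**1. Stable comorbidity.** A vaccinated person with daily rate λ expects 28λ events in each interval. Summed over the vaccinated, the ratio is Σ28λ/Σ28λ = 1, whoever is vaccinated. Simulation with 30% prevalence and hazard ratio 5:

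- raises uptake (0.9 v 0.6): IRR 0.99 (95% CI 0.97-1.01)
- lowers uptake (0.3 v 0.8): 1.00 (0.98-1.03)
- precludes vaccination: 1.03 (0.99-1.07)

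All three are compatible with no bias.

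**2. The event prevents later vaccination with probability q.** Control events fall to (1-q) of their true number, so IRR = 1/(1-q):

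- q = 0.10: 1/0.90 = 1.11
- q = 0.20: 1/0.80 = 1.25
- q = 0.30: 1/0.70 = 1.43

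Simulation gave 1.10, 1.25 and 1.43. The direction agrees with Section 5.2 and bullet 3.

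**3. A transient high-risk state defers vaccination and resolves.** People are out of the state on day 0. Risk days 1-28 lie nearer to day 0 than control days 15-42 before it, so the risk interval is the healthier one. In a two-state model (state present 5-20% of the time, mean duration 14-60 days, hazard ratio 5) the IRR is 0.87-0.96 with the 14-day exclusion and 0.81-0.94 with 28 days. A longer exclusion makes this bias larger.

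**4. The event only delays vaccination.** With the 14-day exclusion, a delay of 14-28 days piles events into the control interval (IRR 0.67), while a delay of 30-90 days empties it (3.33). Extending the exclusion to 28 days gives 1.00 and 1.15.

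**5. Section 5.6, distance between risk and control midpoints.** Under a steady trend in baseline risk, the bias in log IRR grows with this distance. Dose 2 is taken at day 21 or 28 (Table 2), and dose days belong to neither interval. The control midpoint is -28.5 for the 28-day window and -35.5 for ITP (days -56 to -15).

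Example, Pfizer-BioNTech, all doses: risk days 1-20 and 22-49, midpoint (20×10.5 + 28×35.5)/48 = 25.1; gap 25.1 + 28.5 = 53.6.

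| SCRI gap (days) | Janssen | Pfizer-BioNTech | Moderna |
|---|---|---|---|
| 28-day window, all doses | 43 | 54 | 57 |
| 28-day window, first dose | 43 | 39 | 42.5 |
| ITP, all doses | 57 | 68 | 71 |
| ITP, first dose | 57 | 46 | 49.5 |

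First-dose entries use risk midpoints 10.5 (days 1-20) and 14 (days 1-27). In the primary analysis, risk days 1 to R and control days R+1 to 90 have midpoints (R+1)/2 and (R+91)/2, a gap of 45 for any R. The two-dose layouts also give about 45.

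**The case against.** The strongest reply is that bullet 2 and Section 5.2 describe different things: a pre-existing comorbidity in one, the event itself in the other. A reader might infer that bullet 2 simply has the direction reversed. That goes too far. For the fixed comorbidity it describes, the bias is about zero, not upward; Section 5.1 allows either direction; and steps 3 and 4 show that a real downward bias is possible. What stands is that bullet 2 does not describe those mechanisms. Under the transient-state mechanism, which would justify its direction, lengthening the excluded window makes matters worse.

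A reader might also infer that the SCRI would be reported as conservative, or as a lower bound. The documents do not support this. Bullets 1 and 3 say overestimated, Section 5.2 says upwards, and only bullet 2 read alone points the other way.

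On time trends, it would be wrong to say that the secondary and SCRI analyses get no adjustment. Section 5.6 allows modelling of strong time-varying confounding in general, and Section 5.7.3 specifies a regression similar to the primary one. Nor should the Section 5.6 claim be deleted: Section 5.7.4 plans a first-dose SCRI, and for 28-day windows that contrast is closer in time than the primary one.

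Two further points stand. Some risk factors in Section 5.7.1, such as hospitalization in the prior 6 months, are not stable traits, so stratifying by them can be informative. And lengthening the exclusion after a detected drop is already planned.

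**Conclusion.** The point holds as a matter of internal consistency and interpretation. Neither bias stated in bullets 1 and 2 arises from stable comorbidities in this design. Bullet 2's direction also does not fit the depletion that its check is meant to find. Where events prevent vaccination and so deplete the control interval, the IRR is inflated by 1.11 to 1.43 for 10 to 30% depletion. The depletion is assumed, and its real size cannot be derived from the Protocol. A drop confined to the 14 excluded days does no such harm.

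The Section 5.6 statement, judged by midpoint distance, fails for all-dose analyses of two-dose vaccines and for ITP: 54 to 71 days for all-dose two-dose contrasts, 57 for one-dose ITP, and 46 to 49.5 for first-dose ITP, against about 45 in the primary analysis. It holds for first-dose and one-dose 28-day windows (39 to 43 days). These gaps assume dosing exactly at the Table 2 intervals and full follow-up to day 90 after dose 1.

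The primary analysis uses only post-vaccination controls, so its result does not change.

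**What to change.** - Restrict bullets 1 and 2 of Section 5.7.4.1 to event-dependent or time-varying factors, and say that stable comorbidities cancel, as in Section 5.1.
- State direction by mechanism. An event that prevents vaccination gives an overestimate. A transient high-risk state that defers vaccination and resolves can give an underestimate, which a longer excluded window does not cure. An event that only delays vaccination can go either way, depending on the delay.
- Reconcile bullet 2 with Section 5.2 and with its own check. Read a pre-vaccination drop that reaches the control interval as inflating the SCRI and secondary estimates. Use the daily plots across the observation period already planned in Section 5.7.1 to see whether the deficit continues after day 0, which would point to the transient-state mechanism instead.
- Use stratification to study this bias only for recent or changing risk factors.
- Qualify Section 5.6: name the contrasts for which the SCRI is closer in time than the primary analysis.
- List the baseline-risk offset of Section 5.7.2.1 as a sensitivity analysis in Sections 5.7.3.1 and 5.7.4.1 too.

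The cost is text edits and the same offset in two more models. No new data are needed.

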5.8 Statistical Power and Sample Size

Assuming the risk interval ranges from 28 to 56 days within the observation period of 90 days, Table 6 presents the minimum number of observed AESI required for an SCCS study design to detect the risk ratios (RR) detected in CMS Medicare RCA study at 80% power with two-sided alpha=0.05.^{25,26} The AESI-specific RRs following any-dose of Pfizer-BioNTech vaccination was used for power calculation in this study because they reached the statistical threshold in the CMS Medicare RCA study. We assume similar RR for Moderna and Janssen vaccines in this calculation. Given that delays in processing time of claims vary by AESI and that the primary SCCS analysis requires complete data (≥90%) for both post-vaccination risk intervals and post-vaccination control intervals, we plan to start the inferential study for each AESI when the minimum number of AESI is observed. Based on each AESI’s delay distribution of claims, the study anticipates implementing this protocol at the earliest in June 2021 for AMI, PE and ITP and in mid-July 2021 for DIC, when the primary analysis is estimated to be statistically powered for Pfizer-BioNTech and Moderna. For the Janssen vaccine, the analysis will start when a sufficient number of cases following vaccination is accrued.

Table 6. Sample size required to detect the risk ratios (RR) detected in CMS Medicare RCA at 80% power with two-sided alpha=0.05 for an SCCS study

AESI	Length of Risk Intervals (days)	RR*	Estimated Sample Size
Acute Myocardial Infarction (AMI)	28	1.42	281
Acute Myocardial Infarction (AMI)	56	1.42	286
Pulmonary Embolism (PE)	28	1.54	183
Pulmonary Embolism (PE)	56	1.54	191
Disseminated Intravascular Coagulation (DIC)	28	1.91	79

Disseminated Intravascular Coagulation (DIC)	56	1.91	89
Immune thrombocytopenia (ITP)	28	1.44	259
Immune thrombocytopenia (ITP)	56	1.44	265

* Unadjusted association detected in the CMS Medicare RCA study for any dose of Pfizer-BioNTech vaccine.

6 Medical Record Review

During the course of the study, a convenient sample of medical records for each AESI will be retrieved and undergo an adjudication process to assign potential cases identified in claims data as true cases and non-cases, and potentially indeterminate; a clinical case definition based on clinical input from subject matter experts will be used for each AESI. Brighton Case definitions are not available for these events at the time of this protocol development. The study will identify appropriate clinical reviewers to review the redacted medical records and abstracted data to recommend expert case designations.

A sample size of up to 100 adjudicated cases for each safety outcome will result in reasonable precision (10%) to estimate a positive predictive value (PPV) of 0.8. The PPV is defined as the likelihood that a person with the diagnosis code recorded in administrative claims data within a prespecified period actually has the disease (Table 7).

Table 7. Precision of PPVs based on the total sample size and the point estimate

Total Sample Size	PPV Confidence Intervals (CI)					
	True PPV = 0.4	True PPV = 0.5	True PPV = 0.6	True PPV = 0.7	True PPV = 0.8	True PPV = 0.9
50	(0.28, 0.54)	(0.37, 0.63)	(0.46, 0.72)	(0.56, 0.81)	(0.67, 0.89)	(0.79, 0.96)
100	(0.31, 0.50)	(0.40, 0.60)	(0.50, 0.69)	(0.60, 0.78)	(0.71, 0.87)	(0.83, 0.94)
150	(0.33, 0.48)	(0.42, 0.58)	(0.52, 0.67)	(0.62, 0.77)	(0.73, 0.86)	(0.84, 0.94)
200	(0.33, 0.47)	(0.43, 0.57)	(0.53, 0.67)	(0.63, 0.76)	(0.74, 0.85)	(0.85, 0.93)

The study will consider a Quantitative Bias Analysis based on an array of hypothetical parameters informed by PPVs estimated from the outcome validation.²⁷ This analysis will assess the direction, magnitude, and uncertainty associated with systematic errors influencing measures of associations. Details of the analysis will be developed later.

7 Ethical Evaluation

This surveillance activity is conducted as part of the FDA public health surveillance mandate.

8 Quality Assurance and Control

The analyses described in this protocol will be conducted using a well-characterized database, the CMS Medicare database, in which OBE has previously conducted numerous epidemiologic studies. For the

current study, the team has performed quality control measures in the database such as executing checks examining the validity of claims data variables, stability of enrollment and health event trends, and consistency with population selection criteria for the database, if any. In addition, the team has validated codes for identifying individuals who received a COVID-19 vaccination and those who have been diagnosed with an AESI.

Data quality is continuously monitored with every update from the study database to ensure insurance claims representing vaccinations and AESI are captured accurately. As an overall check, the total number of claims newly observed in each data cut will be counted, stratified by care setting and HHS region. If substantial increases or decreases in the rate of claims accrual relative to previous cuts are observed, steps will be implemented to trace the potential causes of the discrepancy, such as by examining regions with accrual different from the national average, examining whether the data cut spans holidays that may reduce service utilization, or identifying providers whose claims submission patterns have changed. The study will also conduct more specific checks on the health care encounters occurring in care settings similar to COVID-19 vaccination or AESI, such as other vaccinations as negative control exposures or hospitalization for external injuries as negative control outcomes. Well-established and validated software such as SAS version 9.4, Stata, and R will be used for statistical analyses.

9 References

1. U.S. Food and Drug Administration. COVID-19 Vaccine Safety Surveillance. <https://www.fda.gov/vaccines-blood-biologics/safety-availability-biologics/covid-19-vaccine-safety-surveillance>, last accessed on 5/7/2021. Published 2021. Accessed.
2. COVID-19 Vaccine Safety Surveillance: Active Monitoring Master Protocol. <https://www.bestinitiative.org/wp-content/uploads/2021/02/C19-Vaccine-Safety-Protocol-2021.pdf>, last accessed on 5/7/2021 Published 2021. Accessed.
3. The 2019 Annual Report of the Boards of Trustees of the Federal Hospital Insurance and Federal Supplementary Medical Insurance Trust Funds. <https://www.cms.gov/Research-Statistics-Data-and-Systems/Statistics-Trends-and-Reports/ReportsTrustFunds/Downloads/TR2019.pdf>, last accessed on 5/7/2021. Published 2019. Accessed.

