4.3 Safety outcomes: Adverse events of special interest (AESI)

Each of the AESI including AMI, PE, DIC, ITP will be assessed separately in the analysis by vaccine brand. The diagnosis of AESI will be identified with International Classification of Diseases, Tenth Revision, Clinical Modification (ICD-10-CM) codes (Appendix Table 1). The settings in which each outcome will be evaluated, as well as the clean (washout) and risk windows for each AESI are described in Table 3. The first occurrence of the event is defined as an incident AESI only if no event was recorded during the preceding pre-defined interval or the clean window. The risk window is defined as an interval post-vaccination during which occurrence of the AESI may be associated with the vaccine exposure. Both clean and risk windows are selected based on the literature and consultation with subject matter experts.

Table 3. AESI, settings, clean windows, and risk windows

AESI	Care Setting	Clean Window	Risk Window
Acute Myocardial Infarction (AMI)	IP	365 days*	1-28 days ^{4,5}
Pulmonary Embolism [#] (PE)	IP, OP/PB	365 days*	1-28 days ⁶⁻⁸
Disseminated Intravascular Coagulation (DIC)	IP, OP-ED	365 days*	1-28 days ⁹
Immune Thrombocytopenia (ITP)	IP, OP/PB	365 days*	1-42 days ^{10,11}

* Selection of clean window duration is based on clinician input.

[#] The PE onset date is determined by the date the PE code is reported in the database.

5 Study Design

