5.4.1 Primary Analysis: SCCS with Post-vaccination Control Intervals

The observation period will start from the vaccination date (day 0) of the first dose, if there are two doses, and extend to day 90. The post-vaccination control interval is defined as all follow-up time during the observation period following either the first or second COVID-19 vaccine dose (for two-dose COVID-19 vaccines) that is outside of the risk interval(s) until day 90 post-vaccination, end of study period, disenrollment, or death, whichever occurs first; while likely uncommon, this includes any time between the end of the first dose risk window and the receipt of a second dose. Figure 1 presents some hypothetical examples in design. Individuals who only accrued data during the risk intervals will be ineligible to be included in the analysis (Section 5.5.1).

Figure 1. Hypothetical examples of SCCS design with post-vaccination control intervals for one-dose and two-dose vaccines

[figure not shown]

Note: The hypothetical risk interval following one dose is up to 28 days. However, the length of the risk and control intervals will vary for each AESI.

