Pulmonary Embolism (PE)	IP, primary diagnosis position
Disseminated Intravascular Coagulation (DIC)	IP
Disseminated Intravascular Coagulation (DIC)	IP, primary diagnosis position
Immune Thrombocytopenia (ITP)	IP
Immune Thrombocytopenia (ITP)	IP, primary diagnosis position

To assess the robustness of risk and control intervals, different lengths of the risk interval and the control interval will be explored with clinical input and consideration of empirical data from temporal clustering by plotting the distribution of incident AESI since vaccination and temporal scans to detect statistical clustering of events post vaccination. Given the potential carry-over effect, we will exclude a range of periods (e.g., 7, 14, and 21 days) after the end of the risk interval from contributing to the control intervals.

To assess the robustness of the analysis to potential violation of the assumption that exposures are independent of outcomes (e.g. AESI post first-dose may delay or preclude administration of the second-dose), a modified SCCS analysis will be conducted which adjusts for censored, perturbed or curtailed post-event exposures.²²

To assess the robustness of the analysis to the potential violation of the assumption that observation time is independent of outcomes (e.g. death post-AESI censors follow up time), a modified SCCS analysis will be conducted which removes the independence assumption.²³

To assess the robustness of the analysis to the potential under-capture of second doses administered by providers who do not submit insurance claims, a sensitivity analysis will be conducted removing projected second-dose exposed time potentially misclassified as control time among patients with only one observed dose. The empirical distribution of exposed time post-second dose will be assessed among patients with two doses, and the corresponding time will be excluded from the control time of patients with only one observed dose.

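### Table 6 sizes ITP at 28 and 56 risk days although the ITP window is 42 days, so starting at the 265-case minimum gives about 74-77% power (Pfizer-BioNTech) and 64-68% (Moderna) for two-dose cases, not 80%

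*Protocol*

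**What the plan says.** Table 3 (Section 4.3) fixes the ITP window per dose: "Immune Thrombocytopenia (ITP) IP, OP/PB 365 days* 1-42 days". The other three outcomes have 1-28 days.

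Section 5.4 ends a first-dose risk interval at the second dose if that dose falls inside it; a full second-dose interval then follows. Table 2 gives dosing intervals of 21 days (Pfizer-BioNTech) and 28 days (Moderna). Section 5.4.1 sets the observation time: "The observation period will start from the vaccination date (day 0) of the first dose, if there are two doses, and extend to day 90".

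Section 5.8 begins "Assuming the risk interval ranges from 28 to 56 days within the observation period of 90 days" and sizes the study for the risk ratios "detected in CMS Medicare RCA study at 80% power with two-sided alpha=0.05". Its ITP rows read "Immune thrombocytopenia (ITP) 28 1.44 259" and "Immune thrombocytopenia (ITP) 56 1.44 265". The numbers are operational: "we plan to start the inferential study for each AESI when the minimum number of AESI is observed". The section expects the primary analysis to be powered for Pfizer-BioNTech and Moderna at that point.

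Section 5.7.2.1 adds a carry-over check for the primary analysis: "we will exclude a range of periods (e.g., 7, 14, and 21 days) after the end of the risk interval".

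**The concern.** Risk intervals of 28 and 56 days suit a 28-day window: one dose gives 28 days, and two doses give at most 56. For AMI, PE and DIC the on-schedule two-dose totals are 21 + 28 = 49 and 28 + 28 = 56 days, both inside the stated range. For ITP neither row matches any vaccine, and the two-dose totals exceed the upper limit of 56.

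This matters because more risk time within a fixed 90 days means less control time. Beyond an even split, the number of cases needed rises quickly. The ITP minimum decides when the analysis starts, and ITP after Pfizer-BioNTech is one of the four signals the study was set up to evaluate. A null ITP result at that minimum would be read as coming from an analysis with 80% power.

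The same shortage of control time affects the longest carry-over exclusion named for the primary analysis.

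**Working it through.** **Inputs.** RR 1.44, two-sided alpha 0.05 and 80% power (Section 5.8, Table 6); 42-day ITP window (Table 3); dose gaps of 21 and 28 days (Table 2); first-dose interval cut at dose 2 (Section 5.4); observation from day 0 to day 90 (Section 5.4.1).

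**Formula.** The protocol cites SCCS sample-size references but prints no formula. The signed-root likelihood-ratio form without age effects was tried. With r = risk days / observation days and D = RR·r + 1 − r:

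- A = 2[(RR·r/D)·ln RR − ln D]
- B = (ln RR)²/A × RR·r(1 − r)/D²
- n = (1.960 + 0.842·√B)²/A
- power at n cases = Φ[(√(n·A) − 1.960)/√B]

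**Reproducing Table 6.** Day 0 to day 90 is 91 days. Rounded up, the formula gives:

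| Outcome | 28 days | 56 days |
|---|---|---|
| AMI, RR 1.42 | 281 | 286 |
| PE, RR 1.54 | 183 | 191 |
| DIC, RR 1.91 | 79 | 89 |
| ITP, RR 1.44 | 259 | 265 |

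All eight entries match. With 90 days the ITP values are 258 and 267. So the table is right for its inputs, and the ITP input is what conflicts with Table 3.

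**ITP risk time under the protocol's rules.** One dose: 42 days. Two-dose Pfizer-BioNTech: 21 + 42 = 63. Two-dose Moderna: 28 + 42 = 70.

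**Worked example (63 of 91 days).** r = 0.6923, D = 1.3046, A = 0.02547, B = 0.9409, so n = 302.7, rounded up to 303. At 265 cases, (√(265 × 0.02547) − 1.960)/√0.9409 = 0.66, which is 74% power.

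**Results at RR 1.44** (ranges cover 91- and 90-day denominators):

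| ITP group | Risk days | Cases for 80% | Power at 265 | Power at 259 |
|---|---|---|---|---|
| One dose | 42 | 237 | 84% | 83% |
| Pfizer-BioNTech, two doses | 63 | 303-308 | 74% | 73% |
| Moderna, two doses | 70 | 375-386 | 64-65% | 63-64% |

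Exact binomial likelihood-ratio power at 265 is 76-77% (Pfizer-BioNTech) and 67-68% (Moderna).

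**One-dose cases in the mix.** If 10-30% of the 265 cases have only one dose (an assumed range), power is about 75-77% (Pfizer-BioNTech) and 67-72% (Moderna).

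**Control days after carry-over exclusion, primary analysis, ITP:**

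| Group | No exclusion | 7 days | 14 days | 21 days |
|---|---|---|---|---|
| One dose | 90 − 42 = 48 | 41 | 34 | 27 |
| Pfizer-BioNTech, two doses | 90 − 63 = 27 | 20 | 13 | 6 |
| Moderna, two doses | 90 − 70 = 20 | 13 | 6 | none (20 − 21 = −1) |

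**The case against.** **The trigger is a floor.** Table 6 gives minimum numbers, nothing caps the analysis at 265, and the protocol reports no accrued ITP count. This stands. A reader might infer that the ITP analysis will be underpowered; the documents do not support that, because the shortfall arises only if the analysis starts at or near the stated minimum. It does not make 265 the right minimum.

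**The planning RR is crude.** It is an unadjusted surveillance estimate, simply assumed for Moderna. By the same formula, 265 cases give 80% power at an RR of about 1.48 (63 days) or 1.55-1.56 (70 days), so for Pfizer-BioNTech the gap is small compared with the uncertainty in the RR. That is fair, but the protocol still states its power at 1.44.

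**The two-dose, on-schedule case is idealised.** One-dose cases raise power, as shown above, though not to 80% at shares of 10-30%. Longer dose gaps or early censoring would lower it.

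**The carry-over point is easily overstated.** A reader might infer that the 21-day run has no control time for two-dose vaccines in general. Only two-dose Moderna cases on the Table 2 interval lose all of it; Pfizer-BioNTech cases keep about 6 days and one-dose recipients 27. The exclusion lengths are given as examples. The secondary analysis plans the same exclusions and adds a 42-day pre-vaccination control interval for ITP, so the run can be estimated there, subject to the reverse-causation bias that Section 5.2 describes.

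**Conclusion.** The point holds for ITP. Table 6 contradicts Table 3, and the ITP numbers that serve as a start trigger do not give the stated 80% power for two-dose cases. Against 265, about 303-308 cases are needed for Pfizer-BioNTech (38-43 more) and 375-386 for Moderna (110-121 more). At 265 cases, power is about 74-77% and 64-68%, a type II error of roughly 23-26% and 32-36% instead of 20%.

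These figures assume RR 1.44, two doses at the Table 2 interval for every case, follow-up to day 90 and an analysis at exactly 265 cases. Janssen is not underpowered: 237 cases suffice and 265 give 84%. The mismatch does not extend to AMI, PE or DIC, whose two-dose totals lie within 28-56 days. The model, the estimand and the type I error are not in question.

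The carry-over point is secondary. In the primary analysis, a 21-day exclusion cannot be estimated from on-schedule two-dose Moderna ITP cases, and for Pfizer-BioNTech it would rest on about 6 control days. Whether day 0 counts as control time is not settled in the text; if it does, the Moderna cases keep that one day.

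**What to change.** 1. In Table 6, replace the two ITP rows with 42, 63 and 70 risk days (237, 303 and 375 cases on the table's own 91-day basis). Amend the stated 28-to-56-day range, and use the brand-specific number as the ITP start trigger. Alternatively, keep 265 and state the power there as about 74-77% (Pfizer-BioNTech) and 64-68% (Moderna), with the assumptions.
2. In Section 5.7.2.1, state for which ITP vaccine groups the 21-day carry-over run can be estimated, or drop that length for two-dose ITP. Extending observation past day 90 is optional and not required; it would trade against the time-varying confounding that Section 5.6 associates with longer control intervals.

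The cost is three table entries and one or two sentences. Claims accrue in any case, so a higher trigger means at most a short delay to the ITP start.
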